Official Title: Elagolix for Fertility Enhancement Clinical Trial (EFFECT) NCT04039204 IRB-Approved Date: 6/1/2023 Study Title: Elagolix for Fertility Enhancement Clinical Trial (The EFFECT Trial)

Principal Investigator: [name] [name] (Wake Health) Co-Investigators: [name] [name] (University of North Carolina, Chapel Hill) and [name], Stanford University

Sponsor or funding source: (e.g. NIH, NICHD)

Background, Rationale and Context

Endometriosis is defined as the presence of endometrial glands and stroma outside the endometrial cavity. It affects at least 176 million women worldwide and over 10 million in the U.S.A., result in in an annual U.S. cost of over \$22 billion. The impact on IVF has not been well studied, since most women with the disease are not counted, and those included in meta-analyses have already been surgically treated. Recent work from our laboratory has identified two endometrial proteins, BCL6 and SIRT1, that are associated with endometriosis and together cause progesterone resistance, the *sine quo non* of endometriosis (Evers-Hoeker et al 2017; Yoo et al, 2018). The over-expression of BCL6 has been shown to be associated with IVF failure (Almquist 2018; Figure 1) and had a high sensitivity and specificity for detection of endometriosis (Ever-Hoeker et al, 2017). Recurrent IVF implantation failure has also been shown to be treatable with suppression of menses using leuprolide acetate, letrozole, or both together (Surrey et al., 2017; Miller et al., 2012; Steiner et al., 2019). Furthermore, treatment of women with elevated BCL6 with surgery or medical suppression for 2 months prior to embryo transfer

(Lupron) improves outcomes compared to controls (Likes et al, 2019).

Figure 1: BCL6 and IVF success. The darker staining for BCL6 provides an indication for the presence of endometriosis. When women entering an IVF cycle were tested, those positive for BCL6 (> 1.4 HSCORE) had a significantly decreased pregnancy rate compared to women

with low BCL6.(Almquist et al., 2018).

Elagolix (Orilissa) is a new generation FDA approved orally active GnRH antagonist that is rapidly reversible, for the treatment of endometriosis and pelvic pain (Taylor et al., NEJM 2018). There have been no randomized controlled trials examining the efficacy of elagolix for the treatment of endometriosis-associated infertility. Given the recent study in Fertility and Sterility demonstrating that IVF outcome prediction using BCL6 and subsequent preliminary data showing benefit using surgery and GnRH agonist therapy (Likes et al., 2019), and data on recurrent implantation failure responding to GnRH agonist and aromatase inhibitors (Steiner et al., 2019), there is adequate rationale to examine the use of this orally active, non-peptide compound (elagolix) for menstrual suppression prior to frozen embryo transfer in women who test positive for SIRT1 and BCL6 and therefore has suspected endometriosis. In addition, during the conduct of this RCT to study elagolix treatment to study pregnancy outcomes and miscarriage

(primary and secondary outcomes), we are collecting blood (estradiol and cytokine measurements) to study the effect of medical suppression on inflammatory biomarkers in blood as well.

Objectives

To perform a prospective, open label randomized controlled trial for women who failed IVF with euploid embryos who have suspected endometriosis based on elevated elevated SIRT1/BCL6, comparing 2 months of elagolix (200 mg BID) to oral contraceptives (orthocylen; OPCs).

Primary clinical objective is to determine methods to improve clinical pregnancy rates in these subjects who later undergo frozen embryo transfer with euploid (genetically tested) embryos.

Justification

standardized frozen embryo cycle (FET) cycle using a single euploid embryo. Eight days after embryo transfer, serum hCG levels will be obtained on day 8 after the FET. Outcomes will be recorded including estradiol, progesterone and hCG measurements and documentation of pregnancy outcomes based on ultrasound. The outcome variables will include 1) cancellation; 2) not pregnant; 3) biochemical pregnancy; 4) ongoing pregnancy (sac with cardiac activity) and 5) live birth rate. Miscarriage rate will be calculated based pregnancy loss/number of pregnancies (not counting biochemical pregnancy).

FET cycles will begin without intervening menstruation. Subjects will begin estrace 2 mg for 4 days, going to 4 mg for 4 days and then back to 2 mg for 4 days. Progesterone in oil IM injections will be started when the lining is > 6 mm and has a trilaminar appearance. Transfer will occur 126 hours after the start of progesterone, which is continued until 10 weeks gestation if pregnant. If the hCG test is negative, POI will be discontinued.

If the FET is delayed for any reason, whatever treatment the subject is on (elagolix or OCPs) will be extended for up to 2 weeks to avoid interruption in treatment prior to embryo transfer.

Design

A prospective randomized open label controlled trial. Primary outcome will be live birth rate, with secondary outcomes including pregnancy rates, miscarriage rates, measures of inflammation, after treatment at the time of frozen embryo transfer.

Programmed FET Cycle

- i. Patients will be advised to call within a week of stopping the last dose of treatment
- ii. On day 3 after stopping, patients should begin taking estradiol 2mg PO BID
- iii. First monitoring visit should be scheduled for cycle day 9-11 and should include E2, P4, LH, and pelvic ultrasound
 - If endometrium is > 7mm and trilaminar, initiation of progesterone may be scheduled to facilitate FET on desired date
 - If endometrium is < 7mm and/or not trilaminar, estradiol should be increased to 2mg PO TID and another monitoring visit should be scheduled in 4-5 days
- iv. Timing of progesterone start
 - 1. If endometrium is > 7mm and trilaminar, initiation of progesterone may be scheduled to facilitate desired FET date
 - 2. In all cases, progesterone should be initiated with the goal of 126 hours of progesterone exposure prior to FET
 - 3. Progesterone to be utilized is progesterone in oil (PIO) 50mg IM daily

- v. Consideration should be given to cycle cancellation in the following circumstances:
 - 1. Endometrium < 7mm after 2-3 weeks of exogenous estradiol
 - 2. Persistent non-trilaminar endometrium after 2-3 weeks of exogenous estradiol
 - 3. Presence of significant fluid in the endometrial cavity
 - 4. If follicular recruitment is noted, conversion to natural cycle FET may be considered

Setting

The EFFECT trial will be conducted at three academic teaching institutions with accredited Reproductive Endocrinology and Infertility (REI) programs involved in In Vitro Fertilization cycles. Wake Forest will be the central IRB and provide data safety monitoring board (DSMB) capabilities for the study.

Subjects selection criteria

Only patients with previous IVF failure who are suspected or known to have endometriosis on the basis of elevated endometrial BCL6 and SIRT1 will be included in this study. The selection criteria includes the use of these two biomarkers as which defines a specific study population of interest. This inclusion of biomarkers was part of an NIH proposal that was submitted to and funded by the NIH. SIRT1 is strongly induced by resveratrol which has been shown to reduce embryo implantation (Ochiai 2019a) and endometrial decidualization (Ochiai 2019b), supporting the biology as outlined in this proposal. We hypothesize that suppression of endometriosis will have the effect of reducing cytokines associated with inflammation which is part of the endometriosis pathogenesis. Each participant will be required to have at least 1 euploid embryo (preimplantation genetic tested and normal) with intentions to transfer that embryo in a frozen embryo transfer (FET) cycle.

• Inclusion Criteria

- 1. Age 18 to 42
- 2. Parity G0 or greater
- 3. $AMH \ge 0.5 \text{ and } \le 10$
- 4. Planning to undergo FET and PGT-A within 1 year of enrollment
- 5. Must have blastocyst(s) by day 6 that were biopsied for PGT-A
- 6. Has a previous endometrial biopsy showing elevated BCL6 and SIRT1 expression.
- 7. Endometrial thickness at time of transfer \geq 6 and \leq 14

• Exclusion Criteria

- 1. Uterine fibroids > 4 cm in size, if intramural
- 2. Polycystic ovary syndrome (PCOS) according with the Rotterdam criteria
- 3. Ovarian failure and subjects receiving donor oocytes/embryos
- 4. Failure to identify at least 1 euploid embryo for FET

- 5. Anti-cardiolipid and/or lupus anti-coagulant abnormalities by history
- 6. Diabetes mellitus (Type I or Type II)
- 7. Untreated hypothyroidism
- 8. Hyperprolactinemia
- 9. BMI \leq 17 and \geq 40
- 10. Uncorrected uterine anomaly
- 11. Women with osteoporosis
- 12. Women with moderate or severe hepatic impairment defined by Child-Pugh Classes B (moderate) and C (severe)
- 13. Women using strong CYP3A inhibitors (e.g. ketoconazole, clarithromycin)
- 14. Women at high risk of thromboembolic disorders including those that smoke, have cardiac valvular disease, atrial fibrillation, hypertension not controlled by medication, and a history of severe migraines.
- 15. Severe renal disease with GFR < 15 ml/min.

Sample Size

Based on previous studies (Likes et al., 2019) we calculated that 50 patients (25 per arm) are required to have a 90% chance of detecting, as significant at the 5% level, an increase in the primary outcome measure from 11% live birth in the OCP group to 50% in the elagolix group. We decided to include 50 subjects per treatment arm (elagolix 200 mg BID vs OCPs) for 2 months, because unlike the Likes study, we are not using a no treatment control arm, and OCPs may have some benefit over no treatment. Having a non-randomized, no treatment control group to follow will allow us some flexibility, however, in comparing outcomes over time.

Enrollment may vary between sites, but we hope to recruit approximately 1/2 of the subjects at our site with the remainder at each of the other 2 sites (UNC and Stanford). We will perform interim analyses after 25 subjects per arm for safety assessment. Based on the 12 months of treatment in the original study (Taylor et al., 2017), safety concerns are minimal. Nevertheless, we will halt the study using the following stopping rules:

- 1) If after 25 subjects per arm, the OCP ongoing pregnancy rate is higher than the treatment arm with elagolix
- 2) There is no difference between the no treatment controls and the elagolix treatment are at 25 patients per arm

We will perform an interim analysis after 25 subjects per arm to recalculate sample size requirements based on the outcomes at that point (Kuman and Chakraborty 2016).

The choice to use oral contraceptives as a comparator group was made based on surveys of potential subjects who voiced concerns about being assigned to a placebo (no treatment) arm. It was felt, and the NIH reviewers agreed, that having an active comparator group would be acceptable. OCPs, while a first line treatment for endometriosis, may not be as suppressive of endometriosis as traditional GnRH agonist therapy, although no head to head comparison studies are available. Finally, the

choice to **not compare 2 doses of elagolix** is based on published results from the Taylor study (Taylor et al., NEJM, 2017) showing a high proportion of subjects in the 150 mg per day dosing group that ovulated and/or menstruated. Bleeding, ovulation or menstruation is a clearly defined problem that would increase inflammation instead of decreasing it, which is the goal of this study.

Interventions and Interactions

Visit 1: Screening and enrollment. Following initial screening of potential subjects with an IVF failure, a positive SIRT1 and BCL6 on endometrial biopsy and available euploid embryos for transfer, patients will meet with the research nurse who will review all inclusion and exclusion criteria and obtain informed consent from eligible patients.

Visit 2 First day of menses. Patients will be instructed to call with the menses at which time an hCG measurement will be made to rule out pregnancy. Subjects will be prepared for their two treatment cycles. Patients will be randomized using computer generated assignments to receive either 200 mg of elagolix twice daily or daily OCPs (Ortho Cyclen). The medications will be formulated into 2 tablets per day to blind the subjects and researchers. The center will call and receive the treatment by means of an interactive voice-response system. The trials will be conducted in accordance with International Conference on Harmonisation guidelines and applicable regulations and ethical principles of the Declaration of Helsinki. All the women provided written informed consent for the study protocol. Women will be instructed to use two forms of non-hormonal contraception; monthly pregnancy tests were performed including an initial hCG test prior to beginning the medication. During the course of two months of treatment subjects will be encouraged to call in and speak to the research nurse or their clinician with any concerns or reports of side effects. Bone mineral or other safety parameters previously performed in the Elaris I-IV studies by Abbvie showed that we should not expect adverse events due to the brevity of the exposure.

Visit 3: All subjects will be seen at 1 month time interval and adverse reactions to the medial treatments reviewed and recorded. The second month of medications will be dispersed at that time. Adverse events will be coded with the use of the Medical Dictionary for Regulatory Activities, versions 19.0. We will use Fisher's exact test to compare the incidence of any adverse event in the elagolix group with the incidence in the OCP group. All reported P values will be considered two-sided, and confidence intervals for safety end points will be considered relevant at the 95% level.

Visit 4: After completion of 2 months of treatment with elagolix or OCPs, subjects will return for collection of blood (serum and plasma) which will be collected, processed and stored at -80° C for later evaluation. Subjects will be prepared for the upcoming FET cycle.

Visit 5: Completion of the study. Patients will return periodically for standardized treatments as part of their FET cycle for endometrial preparation, ultrasound and embryo transfer as dictated by the clinicians in the practice. Outcomes will be recorded and extracted from their SART database for pregnancy included extended follow-up for live birth rate.

Patients experiencing unanticipated problems with the protocol or who experience adverse events such that they do not tolerate the treatment they are assigned, will be allowed to discontinue treatment and be provided the opportunity to use the other treatment if they so choose. The outcomes of such cycles would be collected separately and included as observational data only and not included in the randomized data analysis. Alternatively, they can simply drop out of the study and resume medical therapy as appropriate or pursue frozen embryo transfer as previously planned.

Outcome Variables

The following outcome data will be collected on each subject:

- 1) BCL6/SIRT1 HSCOREs
- 2) hCG level (first)
- 3) Progesterone levels at first hCG measurement (ng/dl)
- 4) hCG level (second)
- 5) Pregnancy outcome (not pregnant, pregnant biochemical, pregnant miscarriage, pregnant ectopic, pregnant ongoing, pregnant delivered, pregnant 2nd or 3rd trimester loss)
- 6) Categorical outcome (pregnant/not pregnant; summary designation)
- 7) Comments related to overall outcomes
- 8) Number of sacs (0, 1, 2, 3)

Independent Variables

The following demographic data will be collected on each subject:

- 1) Age (based on date of birth)
- 2) Weight
- 3) BMI
- 4) Gravidy/Parity
- 5) Randomization group (elaglox, OCPs, non-randomized control)
- 6) Embryo grade
- 7) Number of remaining euploid embryos
- 8) PGT-A results (narrative)
- 9) Endometrial thickness
- 10) Peak estradiol levels (pg/dl)
- 11) Comments regarding embryo transfer
- 12) Embryo transfer physician (name)
- 13) Number of embryos transferred (confirm that 1 was transferred)

Analytical Plan

Statistical analysis: Statistical analyses will be performed using the Student's ttest for data from the two groups. All data will be presented as means \pm SEM. p < 0.05 was considered statistically significant. Fisher's exact test, relative risk, and 95% confidence interval (CI) will be used for comparisons of categorical data.

Independent Variables.

Measurement of hormones. Estrogen, progesterone and hCG assays will be run by the hospital's clinical laboratories using a competitive antibody technology. Venous blood will be drawn into serum separator tubes and taken immediately to the clinical lab for processing (available 24 hours per day).

Results will be analyzed initially using descriptive statistics. Comparison between groups will be done using chi square tests for proportions, and t-tests for continuous variables. Regression analysis will be performed to identify independent outcome predictors. Other inferential statistical analysis will be conducted as appropriate.

Human Subjects Protection

Subject Recruitment Methods

Subjects who failed IVF or FET with a previous endometrial biopsy showing elevated endometrial BCL6 and SIRT1 will be identified as part of ongoing care. We do not discriminate on the basis of race or economic status, although we do have age and BMI cut-off criteria defined in the protocol. Subjects will be approached in the privacy of the clinic and all conversations will be confidential.

- We plan to use a recruitment flyers in the clinic to help motivate and identify willing subjects. A copy of this poster is provided with the submission material for IRB review.
- Privacy will be protected and no records kept until subjects/patients agree to participate in the study?
- If an individual declines participation including randomization any and all documents will be destroyed.

Informed Consent

Signed informed consent will be obtained from each subject by her physician or a clinic research nurse. Consent will be obtained in the CFEM clinical space where patients receive their care from the REI unit. Other centers will use clinical research staff to consent patients in private offices under similar conditions.

Confidentiality and Privacy

Confidentiality will be protected by collecting only information needed to assess study outcomes, minimizing to the fullest extent possible the collection of any information that could directly identify subjects, and maintaining all study information in a secure manner. To help ensure subject privacy and confidentiality, only a unique study

identifier will appear on the data collection form. Any collected patient identifying information corresponding to the unique study identifier will be maintained on a linkage file, store separately from the data. The linkage file will be kept secure, with access limited to designated study personnel. Following data collection subject identifying information will be destroyed 3 years after completion of the study, consistent with data validation and study design, producing an anonymous analytical data set. Data access will be limited to study staff. Data and records will be kept locked and secured, with any computer data password protected. No reference to any individual participant will appear in reports, presentations, or publications that may arise from the study.

Data and Safety Monitoring

The principal investigator and PIs at UNC and Stanford will be responsible for the monitoring of the data and safety of study participants. The principal investigator will be assisted by other members of the study staff. A data safety monitoring board (DSMB) through WFBH will be established to oversee the entire project.

Per FDA request, we will assess suicidal ideation as part of our safety evaluation. At each visit subjects will be asked whether they have had any thoughts of self-harm as part of their encounter or if there has been any change in thoughts that include suicide. This screening will be two part, since this drug has been well studied and suicide risk is considered very low (Taylor et al., 2017). If a subject reports having suicidal ideation, we will use the PHQ-9 survery, commonly used in primary care. This instrument has a sensitivity of 78% and specificity of 70% (Runeson et al, 2017) and refer the individual for psychiatric evaluation. Subjects will be withdrawn from the study based on the outcomes of these two steps if they appear to be affected by either treatment toward self harm.

We will exclude subjects with moderate to severe hepatic or renal disease or osteoporosis. We have added to the consent information on avoidance of pregnancy.

Any pregnancy resulting in live birth that arises while taking active drug (elagolix or OCPs) will be identified and followed up to 1 year for any problems that might arise as a result of exposure as an early fetus.

Excessive or unexpected bleeding may be considered an adverse event since the purpose of this study is to achieve and maintain amenorrhea for subjects prior to their next frozen embryo transfer.

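### Women who switch treatment are left out of the randomised analysis, so live birth is not compared in all women as randomised

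*Combined protocol and SAP*

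**What the plan says.** The Design section describes the trial and its endpoint as "A prospective randomized open label controlled trial. Primary outcome will be live birth rate". Under Interventions and Interactions, Visit 5, the option to change treatment is open to "Patients experiencing unanticipated problems with the protocol or who experience adverse events such that they do not tolerate the treatment they are assigned". These women may stop and, if they wish, take the other treatment. Of them the protocol says: "The outcomes of such cycles would be collected separately and included as observational data only and not included in the randomized data analysis".

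A second route follows: "Alternatively, they can simply drop out of the study and resume medical therapy as appropriate or pursue frozen embryo transfer as previously planned". Nothing is said about how these women are analysed. The same holds for women withdrawn after the self-harm screening in Data and Safety Monitoring.

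The Analytical Plan names methods only: "Fisher's exact test, relative risk, and 95% confidence interval (CI) will be used for comparisons of categorical data", with t-tests, chi-square tests and regression. It defines no analysis population and no rule for missing outcomes.

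Two items bear on the remedy. The assigned arm is a recorded variable, "Randomization group (elaglox, OCPs, non-randomized control", and outcomes have a stated source: "Outcomes will be recorded and extracted from their SART database for pregnancy included extended follow-up for live birth rate".

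**The concern.** Randomisation makes the two groups comparable at the point of allocation. Removing women because of intolerance or problems arising later gives up that protection, since the women removed from one arm need not resemble those removed from the other.

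The protocol itself offers a route by which removal could be related to prognosis. Data and Safety Monitoring says excessive or unexpected bleeding may be treated as an adverse event. The end of the Sample Size section says bleeding would raise the inflammation that treatment is meant to lower. A woman in whom suppression fails, who bleeds and does not tolerate the treatment, could switch and so leave the comparison.

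At stake is the validity of the primary live-birth comparison. With 50 women per arm, a handful of exclusions can matter.

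The explicit rule covers switchers only. Whether it reaches women who stop without switching is unclear, and for drop-outs and withdrawals the plan is silent.

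**Working it through.** **Does the rule remove the woman or only a cycle?** Methods and Measures plans one transfer of a single euploid embryo after two months of treatment. If that cycle is left out, the woman has no other planned cycle to contribute. No section says she stays in her arm's denominator.

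**The plan's own figure.** The planning effect is "an increase in the primary outcome measure from 11% live birth in the OCP group to 50% in the elagolix group", at 90% power and the 5% level. The two-sided unpooled formula gives

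n = (1.960 + 1.282)² × (0.11×0.89 + 0.50×0.50) / 0.39² = 24.03, so 25 per arm.

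This reproduces the stated 25. It assumes every randomised woman is analysed. The increase to 50 per arm is justified by possible OCP benefit, not by switching or drop-out.

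**Bias if switchers are excluded (illustrative).** Assumed: true live birth 30% in both arms, 50 per arm, two-sided Fisher test at p<0.05, exact enumeration of two binomials. With f the fraction excluded from an arm and r the live-birth rate among those excluded:

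retained rate = (0.30 − f·r) / (1 − f).

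Example, f = 0.15 and 0.05, r = 0: 0.30/0.85 = 35.3% and 0.30/0.95 = 31.6%, a false gap of 3.7 points.

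| Excluded (arm A / arm B) | r, both arms | Retained n | False gap (points) | Rejections favouring A / B | Total | Total, no bias, same n |
|---|---|---|---|---|---|---|
| 15% / 5% | 0% | 42 / 48 | 3.7 | 4.39% / 0.80% | 5.2% | 3.9% |
| 15% / 5% | 10% | 42 / 48 | 2.5 | 3.36% / 1.11% | 4.5% | 3.9% |
| 20% / 5% | 0–10% | 40 / 48 | 3.9–5.9 | – | 5.3–7.1% | 3.8% |
| 5% / 3% | 0–10% | 47–48 / 48–49 | 0.4–0.7 | – | within 0.1 point of no-bias total | – |

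With no exclusions (50 / 50) the total is 3.1%.

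- At 15%/5%, if the excluded women have average prognosis (r = 30%) the gap is zero. At r = 50% it reverses, to −2.5 points.
- Equal exclusion does not protect. With 10% excluded from each arm, at 0% versus 30% live birth, the retained rates are 33.3% and 30.0%: a gap of 3.3 points, with rejections split 3.4% to 0.6%.
- The arm losing more women need not gain. Excluding 15% at 25% live birth against 5% at 0% gives 30.9% versus 31.6%.
- Extreme case: base rate 40%, with 10 of 50 women without a birth removed from one arm only. The retained rate is 0.40/0.80 = 50%, a gap of 10 points, and type I error rises from 3.2% to 12.0%.

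**Power if switchers are kept in their assigned arm.** Assume switchers take the full rate of the other treatment, with switching fractions s₁ (elagolix) and s₂ (OCP) and OCP rate c:

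elagolix = (1 − s₁)×0.50 + s₁×c; OCP = (1 − s₂)×c + s₂×0.50.

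Example, 20% in both arms with c = 0.11: 42.2% versus 18.8%, a difference of 23.4 points.

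| Switching, elagolix / OCP | Fisher power, c = 11% |
|---|---|
| none | 99.0% |
| 5% / 3% | 97.4% |
| 15% / 5% | 92.3% |
| 20% / 5% | 88.9% |
| 10% / 10% | 91.0% |
| 15% / 15% | 80.8% |
| 20% / 20% | 66.1% |
| 30% / 30% | 32.1% |

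If the OCP rate were 20% (assumed, since Sample Size allows that OCPs may help), power is 85.3% with no switching, 65.8% at 15%/5% and 39.3% at 20%/20%.

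**The case against.** **The sentence speaks of cycles, not women.** A switcher could in principle stay in her arm's denominator as a non-birth, since cancelled and not-pregnant cycles are listed outcomes. The bias table would then not apply. But no section says this, and it would record actual births as failures, so the sentence needs correcting on either reading.

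**The size may be trivial.** Exposure is about two months, Visit 2 expects few adverse events, and no switching rate is given. At 5%/3% exclusion almost nothing changes. At 15%/5% the total error stays near the nominal 5%, although it is skewed to one side. Nothing in the documents shows that switchers do worse: the bleeding text was written to justify the choice of dose, and switching also requires intolerance or an unanticipated problem. All this stands. The case rests on the rule, not on a demonstrated size.

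**The increment is unstable.** Excluding 15% and 5% leaves 42.5 and 47.5 women. At 42/48, bias adds about 0.6–1.3 points to the total error; at 43/47 the totals are 4.75–5.55% against 3.87%, so it adds about 0.9–1.7. This is fair, and the added error should be read as approximate.

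**Harm and cost use different assumptions.** The bias table mainly gives switchers a poor prognosis, while the power table gives them the full rate of the other treatment. The two cannot be netted against each other.

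**Blinding.** Methods and Measures and Design describe an open trial, yet Visit 2 describes tablets formulated to blind. These passages must be reconciled. The point does not depend on it, because tolerability can differ between arms under blinding too.

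**Conclusion.** The concern holds and should be corrected before the primary analysis. As written, the plan leaves randomised women out of the live-birth comparison because of a post-randomisation event, and nothing elsewhere restores them. Confidence is high that the rule exists for switchers; no exclusion is claimed for drop-outs or withdrawals.

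The size is unknown. Under the stated assumptions the false gap runs from zero or below 1 point, when switching is rare or unrelated to prognosis, to about 4–6 points at 20%/5% exclusion with poor prognosis among those excluded. The direction cannot be predicted.

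**What to change.** Replace the excluding sentence with:

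*The primary analysis of live birth from the first frozen embryo transfer after randomisation includes every randomised woman in her assigned arm, whatever treatment she took, stopped or switched to; outcomes collected after a switch count in the assigned arm.*

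Then add to the Analytical Plan:

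- Keep the analysis without switchers, labelled supportive.
- Report stops, switches and drop-outs by arm, with reasons.
- State how women with no transfer are counted. Under the wording above they have no birth from a first transfer; a birth from a pregnancy begun on study drug needs its own stated rule.
- For drop-outs and withdrawals, seek the live-birth outcome where consent allows.
- Prespecify how unknown outcomes are handled, with complete-case and best/worst-case sensitivity analyses. Analysis by assigned arm does not by itself remove bias from missing outcomes, and counting unknowns as no birth could misclassify births after a transfer elsewhere.

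No treatment or switching rule changes. For switchers this is a wording change, because their outcomes and assigned arm are already recorded; follow-up of drop-outs may need consent wording.

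The real cost is dilution. Power stays at about 89–97% when switching is low or mostly in the elagolix arm, but drops sharply with heavy switching in both arms. Excluding 20% of each arm would keep nominal power of 96.6% (40 versus 40), but only if exclusion is unrelated to prognosis. The interim sample-size recalculation already planned at 25 per arm should therefore use rates in women as randomised.

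### No baseline-adjusted live-birth comparison is prespecified; adding age and pre-treatment BCL6 HSCORE would be a cheap improvement with a small, assumption-dependent gain

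*Combined protocol and SAP*

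**What the plan says.** The Design section states: "Primary outcome will be live birth rate, with secondary outcomes including pregnancy rates, miscarriage rates, measures of inflammation". Under Sample Size, "50 patients (25 per arm) are required to have a 90% chance of detecting, as significant at the 5% level", an increase "from 11% live birth in the OCP group to 50% in the elagolix group". The plan then enrols 50 per arm because the oral contraceptive comparator may do better than no treatment.

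No test is tied to live birth by name. As a binary outcome it falls under two statements in the Analytical Plan: Fisher's "exact test, relative risk, and 95% confidence interval (CI) will be used for comparisons of categorical data", and "Comparison between groups will be done using chi square tests for proportions, and t-tests for continuous variables". Both are unadjusted. The plan also mentions a regression to find predictors of outcome, but names no outcome or covariates for it and does not say that it yields an adjusted treatment effect.

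Age heads the Independent Variables list. "BCL6/SIRT1 HSCOREs" head the Outcome Variables list, but inclusion criterion 6 requires a previous biopsy that shows elevation of both markers, and Visit 4, after treatment, collects only blood. The HSCOREs are therefore in effect baseline values. This is an inference; the plan does not say so. Visit 2 describes computer-generated assignment at a three-site trial and mentions no stratification factors.

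**The concern.** With 50 women per arm and no described stratification, age or HSCORE can differ between arms by chance. Nothing in the planned primary comparison takes account of such a difference or uses the outcome variation that these variables may explain. If an imbalance appeared, adjustment would have to be chosen after outcomes were seen. The Independent Variables list mixes baseline items with items measured during the transfer cycle, such as endometrial thickness and peak estradiol, so a later choice could pick up a post-treatment variable. Naming two pre-treatment covariates in advance removes that freedom and may improve precision somewhat.

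**Working it through.** **Inputs from the protocol.** 11% v 50%; 5% level; 90% power; 25 per arm calculated, 50 per arm planned. Sample Size does not state sidedness. I take it as two-sided from the safety text under Visit 3: "All reported P values will be considered two-sided".

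**Inputs assumed.** Prognostic strength is not in the documents. I let the log-odds of live birth vary by 0 to 1.0 per SD of a combined covariate (odds ratio 1.0 to 2.7). An oral contraceptive rate of 25% is also an assumption, chosen because the plan allows for some benefit but gives no figure.

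**1. The plan's own figure.** Unpooled formula:

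n = (1.960 + 1.282)² × (0.11×0.89 + 0.50×0.50) / 0.39² = 24.03, so 25 per arm. The stated size reproduces.

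**2. Unadjusted power at 50 per arm.** Power = Φ{[d − 1.96√(2p̄q̄/n)] / √[(p₁q₁ + p₂q₂)/n]}.

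- 11% v 50%: (0.39 − 1.96×0.0921)/0.0834 = 2.51, power 0.994.
- 25% v 50%: (0.25 − 1.96×0.0968)/0.0935 = 0.64, power 0.740.

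**3. Adjusted power by effective sample size.** If the covariates explain a share R² of outcome variance, n becomes 50/(1 − R²).

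| R² | effective n | 11% v 50% | 25% v 50% |
|---|---|---|---|
| 0 | 50.0 | 0.994 | 0.740 |
| 0.02 | 51.0 | 0.995 | 0.749 |
| 0.05 | 52.6 | 0.996 | 0.762 |
| 0.10 | 55.6 | 0.997 | 0.785 |
| 0.15 | 58.8 | 0.998 | 0.808 |
| 0.20 | 62.5 | 0.999 | 0.831 |

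**4. Simulation at 25% v 50%.** 4,000 trials per row, one covariate, risk difference standardised from a logistic model, normal reference. Simulation error is about 0.7 points.

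| Odds ratio per SD | variance, adjusted/crude | crude power | adjusted power |
|---|---|---|---|
| 1.0 | 1.01 | 0.752 | 0.752 |
| 1.35 | 0.99 | 0.753 | 0.763 |
| 1.65 | 0.95 | 0.750 | 0.767 |
| 2.2 | 0.89 | 0.754 | 0.800 |
| 2.7 | 0.85 | 0.762 | 0.830 |

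A variance ratio of 0.85 corresponds to R² of 0.15, so the R² = 0.20 row in step 3 assumes more than the strongest case here.

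**5. Standard error with two covariates.** At 25% v 25% and 50 per arm, the uncorrected influence-function standard error rejected a true null in about 5.6–6.7% of trials. A degrees-of-freedom correction brought this to about 4.9–5.7%. Part of any uncorrected power gain is therefore not real. With the correction, the gain at 25% v 50% is about 0 to 6 points. Covariates with no prognostic value cost about 1–2.5% in variance. At 11% v 11% the logistic fit failed in about 0.5–0.8% of trials at 50 per arm, and in about 11% at 25 per arm.

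**6. Chance imbalance.** A standardised baseline difference between arms has SD √(2/50) = 0.20, so it exceeds 0.25 SD in 21% of trials. With log-odds 0.5 per SD, the shift in the crude difference is about 0.5 × imbalance × p(1 − p).

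- One-SD imbalance, p = 0.30: 0.5×0.20×0.21 = 2.1 points.
- 95% limit, p = 0.30: 1.96×2.1 = 4.1 points.
- 95% limit, p = 0.11: 1.96×0.5×0.20×0.0979 = 1.9 points.

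The crude difference at 25% v 50% has a standard error of √[(0.1875 + 0.25)/50] = 9.4 points.

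**The case against.** The strongest case against is that an unadjusted comparison of randomised arms is a legitimate choice. Its standard error already allows for chance imbalance, so its type I error and confidence interval need no repair. That stands. A reader might infer from the imbalance figures that the planned result would be biased or invalid; the arithmetic does not support that. A typical shift of about 2 points lies well inside a standard error of 9.4.

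A reader might also infer a material loss of power. At the plan's stated rates there is none to speak of. Elsewhere the loss rests on an unknown. The Background contrasts BCL6-positive with low-BCL6 women, whereas every woman enrolled is elevated on both markers. The range is truncated, and the documents do not show that the level of HSCORE predicts live birth among positives. They also give no age effect on live birth with euploid embryos. This objection stands and sets the size of the point.

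Nor is adjustment entirely free or automatically safe at this sample size, as the null rejection and convergence results show. That also stands, and the fix has to deal with it.

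The planned regression does not answer the point. Its stated purpose is to find predictors, and it has no defined role in the treatment comparison.

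**Conclusion.** The point holds as a cheap, optional improvement. The primary live-birth comparison is unadjusted, no stratification is described, and no adjusted treatment effect is prespecified, although two pre-treatment covariates are to hand. The gain is under 1 point of power at 11% v 50%. It is about 0 to 6 points at an assumed 25% v 50% with a corrected standard error, over an assumed prognostic range from none to an odds ratio of 2.7 per SD. It also rests on the HSCOREs coming from the qualifying biopsy.

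Two neighbouring matters are separate and not part of this gain. One is the conflict between Fisher's exact and chi-square tests (exact power 0.675 v 0.745 at 25% v 50%). The other is the exclusion of women who switch treatment from the randomised analysis.

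**What to change.** In the Analytical Plan, before any outcome by arm is seen:

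- Make the primary analysis the live-birth relative risk, which is the plan's stated measure, together with the risk difference, each with a 95% CI. Standardise both over the analysed sample from a logistic model with arm, age and pre-treatment BCL6 HSCORE, both continuous.
- State that the HSCORE is the value from the qualifying biopsy.
- Use a degrees-of-freedom-corrected standard error with a t reference, or a re-randomisation test.
- Name the crude comparison as the fallback if the model does not converge.
- Report the crude Fisher's exact test as a sensitivity analysis.

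This costs protocol wording and a few lines of code, with no new data. The downsides are slightly more complex reporting, about 1–2.5% in variance if the covariates are not prognostic, and a small risk of non-convergence at low event rates, which is larger at the 25-per-arm interim.
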